2.2. Randomization and Blinding

This is a non-randomized, open-label study and there is no blinding.

2.3. Data Monitoring Committee

During the conduct of this study, an internal safety committee will review accumulating safety data on a regular basis (or adhoc if required, as detailed in the internal safety committee charter) to ensure the continuing safety of the study patients and study conduct issues. Additional details are outlined in Section 3.6.1 of the protocol.

2.4. Sample Size and Power Considerations

This is an open-label study. The sample size for this study is not based on statistical considerations; hence, only descriptive statistics will be presented. Up to 650 patients who completed the PRIDE-HD, exited from Open PRIDE-HD global or local amendments, completed any future safety and efficacy clinical trials of pridopidine, or transitioned from the ongoing Open-HART study and met patient exclusion/inclusion criteria will be enrolled.

2.5. Sequence of Planned Analyses

2.5.1. Planned Interim Analyses

There will be no formal interim analysis for this study.

2.5.2. Final Analyses and Reporting

All analyses identified in this SAP will be performed after the end of study as defined in the study protocol.

This SAP and any corresponding amendments will be approved before database lock, in accordance to SOP GBP_RD_702 (Statistical Analysis Plan).

The data collected in the digital health sub-study will be analyzed and reported separately from this SAP by [REDACTED]

3. ANALYSIS SETS

3.1.1. Intent-to-Treat Analysis Set

The intent-to-treat (ITT) analysis set will include all enrolled patients, regardless of whether or not a patient took any study drug. A patient is considered enrolled according to the status reported in the database.

3.1.2. Safety Analysis Set

The safety analysis set will include all patients who receive at least 1 dose of study drug.

3.1.3. Full Analysis Set

The full analysis set will include all patients in the ITT analysis set who receive at least 1 dose of study drug and have a baseline and at least 1 post-baseline UHDRS-TMS assessment.

4. GENERAL ISSUES FOR DATA ANALYSIS

4.1. General

Descriptive statistics for continuous variables include n, mean, standard deviation (SD), standard error (SE), median, minimum, and maximum. Descriptive statistics for categorical variables include patient counts and percentages, missing category will be displayed as appropriate.

4.2. Specification of Baseline Values

For patients from the PRIDE-HD study, the baseline value is the last observed data prior to the first dose of study drug in this study. For patients from the ACR16C015 (OpenHART) study, the baseline value is the last observed data prior to the first dose of study drug in the Open-HART study.

ECGs at screening are performed in triplicate. If the screening value has to be used for the baseline value for patients from the PRIDE-HD study, then for the ECG variables use the mean of 3 measurements as the baseline value. For the ECG finding, use “abnormal” as the baseline value if any of the responses are abnormal, and “normal” as the baseline value if all responses are normal.

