2.1. General Design

This is a multicenter, open-label study to evaluate the safety, tolerability, and efficacy of pridopidine treatment at a dosage of 45 mg bid in adults with HD. The study will consist of a screening period up to 2 weeks, followed by an open-label treatment period.

The assessments and procedures performed during each study visit are detailed in Section 3.12 of the protocol.

Up to 650 patients from the PRIDE-HD, Open PRIDE-HD, Open-HART, or future safety and efficacy clinical trials of pridopidine studies are planned to be enrolled to receive a total daily dose of 90 mg pridopidine (45 mg bid) for the duration of the study.

If medically necessary (eg following discussion with the medical monitor), the patient may be allowed to de-escalate to a dose of 22.5 mg bid. The start date and reason for de-escalation will be entered into the electronic case report form (eCRF).

In addition, patients who have already completed their defined study period under Open PRIDE-HD global or local amendments and have discontinued treatment with pridopidine can be re-enrolled and re-enter the Open PRIDE-HD study. A repeat, 2nd screening and baseline visit will be scheduled after completion of the End of Study (EoS) visit. These patients will complete the repeated (2nd) screening and baseline visit assessments (including meeting all eligibility criteria, see procedures for V1 and V2), and undergo a 1-week titration period and resume attendance of the study visits from the point at which they exited.

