6. EFFICACY ANALYSIS

6.1. General

The ITT analysis set will be used for all study population summaries unless otherwise noted. Summaries will be presented for all patients.

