7. SAFETY ANALYSIS

7.1. General

The safety analysis set will be used for all study population summaries unless otherwise noted. Summaries will be presented for all patients.

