7.4. Clinical Laboratory Tests

Laboratory test results will be presented in standard international (SI) units.

Summary statistics for serum chemistry, hematology, and urinalysis laboratory tests will be presented at baseline and each visit. Laboratory tests values and changes from baseline to each visit will be summarized using descriptive statistics.

Shifts (below, within, and above the normal range) from baseline to each visit will be summarized using patient counts.

The incidence of potentially clinically significant abnormal values will be summarized for laboratory tests using descriptive statistics with the criteria specified in [Table 1](#). These summaries will include all postbaseline values (including scheduled, unscheduled, and early termination visits).

Table 1: Criteria for Potentially Clinically Significant Laboratory Values

| Test | Criterion value |
|-------------------------------------|---|
| Serum chemistry | |
| Alanine aminotransferase (ALT) | ≥3x ULN |
| Aspartate aminotransferase (AST) | ≥3x ULN |
| Alkaline phosphatase | ≥3x ULN |
| Gamma-glutamyl transpeptidase (GGT) | ≥3x ULN |
| Lactate dehydrogenase (LDH) | ≥3x ULN |
| Blood urea nitrogen (BUN) | ≥10.71 mmol/L |
| Creatinine | ≥177 μmol/L |
| Uric acid Men | ≥625 μmol/L |
| Women | ≥506 μmol/L |
| Bilirubin (total) | ≥34.2 μmol/L |
| Hematology | |
| Hematocrit Men | <0.37 L/L |
| Women | <0.32 L/L |
| Hemoglobin Men | ≤115 g/L |
| Women | ≤95 g/L |
| White blood cell (WBC) counts | ≤3 x 10 ⁹ /L ≥20 x 10 ⁹ /L |
| Eosinophils | ≥10% |
| Absolute neutrophil counts (ANC) | ≤1 x 10 ⁹ /L |
| Platelet counts | ≤75 x 10 ⁹ /L ≥700 x 10 ⁹ /L |
| Urinalysis | |
| Blood (HGB) | ≥2 unit increase from baseline |
| Glucose | ≥2 unit increase from baseline |
| Total protein | ≥2 unit increase from baseline |

ULN=upper limit of normal

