7.5. Vital Signs

Summary statistics for pulse, blood pressure (supine/sitting and standing), body temperature, weight, and orthostatic blood pressure (supine/sitting – standing value) will be presented at baseline and each visit. Vital signs values and changes from baseline to each visit will be summarized using descriptive statistics.

The incidence of potentially clinically significant abnormal values will be summarized for vital signs using descriptive statistics with the criteria specified in [Table 2](#). These summaries will include all postbaseline values (including scheduled, unscheduled, and withdrawal visits). Note that in order to qualify as potentially clinically significant abnormal, a value needs to meet both criteria below: ie, have a value beyond the criterion value and a change of at least the magnitude specified in the change relative to baseline column.

Table 2: Criteria for Potentially Clinically Significant Vital Signs

| Vital Sign | Criterion value | Change relative to baseline |
|--------------------------|-----------------|-----------------------------|
| Pulse | ≥120 bpm | Increase of ≥15 |
| | ≤50 bpm | Decrease of ≥15 |
| Systolic blood pressure | ≥180 mm Hg | Increase of ≥20 |
| | ≤90 mm Hg | Decrease of ≥20 |
| Diastolic blood pressure | ≥105 mm Hg | Increase of ≥15 |
| | ≤50 mm Hg | Decrease of ≥15 |
| Body temperature | ≥38.3°C | Change of ≥1.1°C |
| Orthostatic SBP (mmHg) | >= 20 mmHg | |
| Orthostatic DBP (mmHg) | >= 10 mmHg | |

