7.6. Electrocardiography

Shifts (normal and abnormal) from baseline to overall finding and each visit will be summarized using patient counts. For overall finding, the summary will use the worst postbaseline finding for the patient (the abnormal finding if there are both normal and abnormal findings). Summary statistics for ECG variables will be presented at baseline and each visit. Actual values and changes from baseline to each visit will be summarized using descriptive statistics.

The incidence of potentially clinically significant abnormal values for ECG variables will be summarized using descriptive statistics with the criteria specified below.

- QTcF values >450 msec or >480 msec or >500 msec.
- QTcF change from baseline values >30 or >60.
- PR change from baseline ≥25% and value >200.
- QRS change from baseline ≥25% and value >110.
- Heart rate value <60 bpm or >100 bpm.

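### SAP 4.2 gives Open-HART and PRIDE-HD patients different baselines, and the plan pools their changes, so a pooled by-visit change is not change over the weeks on its label

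*SAP*

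**What the plan says.** SAP 4.2 sets two reference points. A PRIDE-HD patient is compared with the last value before the first dose in this study. For an Open-HART patient, "the baseline value is the last observed data prior to the first dose of study drug in the Open-HART study".

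The analysis sections do not carry that distinction forward. For efficacy, SAP 6.1 states that "Summaries will be presented for all patients", and SAP 6.2 asks for actual values and changes from baseline at each visit. For safety, SAP 7.1 states: "The safety analysis set will be used for all study population summaries unless otherwise noted. Summaries will be presented for all patients". Laboratory values, vital signs and ECG variables are then summarised as change from baseline by visit (SAP 7.4 to 7.6). For laboratory tests, "Shifts (below, within, and above the normal range) from baseline to each visit will be summarized using patient counts". None of these summaries is split by source study.

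Some safety criteria also use the baseline but are incidences without a visit label. SAP 7.6 lists "QTcF change from baseline values >30 or >60" and relative changes in PR and QRS. SAP 7.4 has increases in urinalysis results. Under SAP 7.5, most vital-sign measurements must "have a value beyond the criterion value and a change of at least the magnitude specified in the change relative to baseline column".

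Three smaller points concern the same rule:

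- SAP 6.2 refers PBA-s domain scores to the baseline of this study, while PBA-s totals fall under the general rule in 4.2.
- SAP 2.4 admits patients who "completed any future safety and efficacy clinical trials of pridopidine", a group that 4.2 does not mention.
- SAP 2.1 lets patients who have left the study re-enter, attend a second baseline visit and "resume attendance of the study visits from the point at which they exited".

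**The concern.** Readers of an extension study take a column headed Week 52 change to mean change over 52 weeks. Under SAP 4.2 that is true of the PRIDE-HD patients only. For Open-HART patients the same cell holds 52 weeks plus all their time in the earlier study. In a progressive disease the pooled mean then depends partly on how many Open-HART patients are in the cell and how long they had been in Open-HART. Neither is visible in the table.

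Protocol 9.5.2 says the by-visit changes are there to detect trends, so reading them is their whole purpose. No test is planned, so no error rate is at stake. What is at stake is whether the pooled changes mean what their labels say.

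**Working it through.** **No planned figure to reproduce.** The sample size is a cap without a statistical basis (SAP 2.4). The check is a comparison of sections, followed by an illustration of size.

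**Elapsed time under one label.** Let D be the years between the Open-HART baseline and entry to this study (not given; assumed 1, 3 or 5). Elapsed time at the Week 52 label is:

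- PRIDE-HD: 52 weeks.
- Open-HART: 52 + 52 × D = 104, 208 or 312 weeks.

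**Shift in the pooled mean.** Let f be the Open-HART share of patients in the cell, and r the yearly change in UHDRS-TMS, taken as linear and equal in both groups. At t years in this study:

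- pooled mean change = (1 − f) × r × t + f × r × (t + D) = r × t + f × D × r
- shift = f × D × r

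The documents give none of f, D or r. Assumed values:

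| Case | f | D (years) | r (points/year) | Shift (points) |
|---|---|---|---|---|
| Central | 10% | 3 | 3 | 0.9 |
| f varied | 5% to 30% | 3 | 3 | 0.45 to 2.7 |
| D varied | 10% | 1 to 5 | 3 | 0.3 to 1.5 |
| r varied | 10% | 3 | 2 to 4 | 0.6 to 1.2 |
| Joint low | 5% | 1 | 2 | 0.1 |
| Joint high | 30% | 5 | 4 | 6.0 |

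**Drug effect at baseline.** A drug effect of the same size in both groups cancels. If the effect carried over into the two baselines differs by up to c = 3 points (the size of effect cited in Protocol 1.5.1), the central shift becomes f × (D × r ± c) = 0.10 × (9 ± 3) = 0.6 to 1.2.

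**Visit-to-visit trend.** If f is the same at two visits, the shift cancels in their difference. If f moves from 10% to 15%, the difference changes by (0.15 − 0.10) × 3 × 3 = 0.45 points.

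**Criteria without a week label.** The change-based criteria for QTcF, PR, QRS, vital signs and urinalysis carry no elapsed time to misread. They do pool two reference points. The documents give nothing from which to derive a bias in any of them.

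**Re-entrants.** Suppose a patient leaves at Week 104 and returns after 26 weeks (an assumed gap). The change labelled Week 130 spans 130 + 26 = 156 weeks from the first baseline, or 130 − 104 = 26 weeks from the second. The choice matters, so it should be written down.

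**The case against.** The strongest reply is that the Open-HART rule is deliberate and sound. Protocol 3.1 (notes to Figure 1) says these patients continue the same dose with no washout, so a Visit 2 value is an on-drug value. PRIDE-HD patients have a 2-week washout (Protocol 1.4.3). For drug safety, going back to a value before Open-HART dosing is reasonable. This stands. It justifies a different reference point, but not an unlabelled pool of the two.

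Other parts of the defence also stand and limit the point:

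- A reader might infer that the safety results, and so the primary objective, are biased. The documents do not support that. The illustration rests on motor worsening, and nothing in them says that QTcF, laboratory values or vital signs drift with time.
- A reader might infer that all six efficacy scales are affected. The documents do not show which scales were measured before the first Open-HART dose. Where there is no such value, Open-HART patients add nothing to the change.
- A reader might set 0.9 points against the effect of about 3 points in Protocol 1.5.1. That figure is a difference from placebo, and this study makes no such comparison.
- A reader might infer that re-entrants have no baseline. They return to the same study and resume its visit numbering. Day 1 in SAP 4.5 is the first dose, so the natural reading of 4.2 keeps their first-entry baseline. This is an ambiguity, because the role of the second baseline visit is not stated.
- Future-trial patients do lack a rule, but they are prospective. The supplied protocol (up to 300 patients) does not name them; only the SAP (up to 650) does. This is a missing detail.

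**Conclusion.** The point holds for by-visit changes. Wherever Open-HART patients contribute, pooled changes in efficacy scores, laboratory values and shifts, vital signs and ECG variables mix elapsed times under one week label. They cannot be read as change over that number of weeks. This follows from the text for any Open-HART share above zero.

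The size is not known. It is share × years in Open-HART × yearly change, and all three are assumed. The central illustration is 0.9 UHDRS-TMS points, with joint extremes of 0.1 and 6.0, so the documents cannot say whether the effect is trivial or material.

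For the change-based safety criteria the conclusion is narrower: they pool two reference points, and no bias has been shown. Actual values by visit, adverse event summaries, C-SSRS, discontinuation and absolute limits (including QTcF and heart rate) are not affected. Visit-to-visit trends are unaffected while the Open-HART share stays constant. Efficacy is exploratory and descriptive, so the harm is misinterpretation. It is worth correcting because the correction is cheap.

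**What to change.** In SAP sections 6 and 7:

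- Present every change-from-baseline summary by parent study, with the baseline stated in the table.
- Keep the pre-Open-HART baseline for Open-HART safety changes, and report the time from that baseline to entry (n, median, range).
- If a pooled column is kept, label it as mixed baseline and do not interpret it as change over the stated weeks.
- For efficacy, optionally add Open-HART change from this study's Visit 2, labelled as on drug at baseline.
- In SAP 6.2, use one named baseline for both PBA-s totals and domain scores.

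As clarifications in SAP 4.2:

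- State a baseline for patients from future trials. Without one, their membership of the full analysis set is also undefined, because SAP 3.1.3 requires a baseline UHDRS-TMS.
- Confirm that re-entrants keep the baseline before their first dose in this study, or say how the second baseline is used.

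The cost is SAP wording and extra table columns. Some cells will be small, chiefly Open-HART and any future-trial group. Study conduct does not change.

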4.3. Scoring for Rating Scales

A detailed description for all rating scales below can be found in the protocol.

The UHDRS comprises a broad assessment of features associated with HD. It is a research tool which has been developed to provide a uniform assessment of the clinical features and course of HD. The TMS component of UHDRS comprises 31 assessments from the 15 items of the UHDRS. The UHDRS-TMS is calculated as the sum of the 31 motor assessments.

The mPPT quantifies the patient's performance in physical tasks. It is a standardized 9-item test that measures the patient's performance on functional tasks. Both the speed and accuracy at which the patients complete the items are taken into account during scoring. The maximum score of the test is 36, with higher scores indicating better performance. The mPPT total score calculated as the sum of the 9 items. See [Appendix A](#) for details of the scoring method for the mPPT total score.

The TFC scale of the UHDRS assesses 5 functional domains associated with disability (occupation, finances, domestic chores, activities of daily living, and care level). Scores on each item range from 0 to either 2 or 3 (eg, Occupation: 0 = unable, 1 = marginal work only, 2 = reduced capacity for usual job, 3 = normal). The 5 items are summed to yield a TFC total score, which ranges from 0 to 13, with greater scores indicating higher functioning.

The SF-12[®] is a multipurpose short-form generic measure of health status. The 12 items in the SF-12[®] are a subset of those in the SF-36[®]; SF-12[®] includes 1 or 2 items from each of the 8 health concepts. The SF-12[®] total score is calculated as the sum of the 12 items.

The PBA-s is a brief semi-structured interview covering the most common behavioral and psychiatric manifestations of HD. The interview is not restricted to a single construct, but rather

covers several broad symptom domains relevant to HD, comprising 11 items. Each symptom is rated for both severity and for frequency on a 5-point scale. Severity and frequency scores are multiplied (after setting all values outside the range of 0-4 to missing) to produce an overall 'PBA score' for each symptom. The PBA total score is the sum of all PBA scores across the 11 symptoms.

Q-Motor assessments will be performed only in those sites that have access to the devices needed to perform the assessments and, where this is the case, only in those patients who are capable of performing the assessments. All Q-Motor assessments are based on the application of pre-calibrated and temperature-controlled force transducers and 3-dimensional position sensors with very high sensitivity and test-retest reliability across sessions and sites in a multicenter clinical study. If a certain test has a left and right value, an average value will be calculated from the test.

4.4. Handling Withdrawals and Missing Data

For all variables, only the observed data from the patients will be used in the statistical analyses, i.e., there is no plan to estimate missing data.

For the TMS component of the UHDRS, if responses to 1 assessment up to 25% of assessments are missing, the missing responses will be replaced by the average of the remaining responses within the TMS component. If responses to more than 25% of the assessments are missing, the missing responses will not be replaced and the UHDRS-TMS will be set to missing.

For mPPT, item 1 (balance tasks), item 4 (put on and remove a jacket), and item 6 (turn 360 degrees) have to be calculated before calculating the total score. For all 3 items, if any questions are missing then the missing responses will not be replaced and the item will be set to missing. After calculating items 1, 4, and 6, if responses to 1 item up to 25% of items are missing, the missing responses will be replaced by the average of the remaining responses. If responses to more than 25% of the items are missing, the missing responses will not be replaced and the total score will be set to missing.

For the TFC scale of the UHDRS, if responses to 1 item up to 25% of items are missing, the missing responses will be replaced by the average of the remaining responses within the TFC scale. If responses to more than 25% of the assessments are missing, the missing responses will not be replaced and the UHDRS-TFC will be set to missing.

For SF-12, if responses to 1 item up to 25% of items are missing, the missing responses will be replaced by the average of the remaining responses. If responses to more than 25% of the items are missing, the missing responses will not be replaced and the total score will be set to missing.

For PBA-s, the severity x frequency items need to be calculated before calculating the total score. If either the severity or frequency value is missing then the item will be equal to the nonmissing value. After calculating the items, if responses to 1 item up to 25% of items are missing, the missing responses will be replaced by the average of the remaining responses. If responses to more than 25% of the items are missing, the missing responses will not be replaced and the total score will be set to missing.

For Q-motor assessments, if either the left or right value is missing for a certain test, then the average value will be equal to the nonmissing value.

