6.2. Efficacy Endpoint and Analysis

The efficacy endpoints are as follows:

- UHDRS-TMS change from baseline to each visit that this is measured.
- mPPT total score change from baseline to each visit that this is measured.
- UHDRS-TFC change from baseline to each visit that this is measured.
- SF-12 total score change from baseline to each visit that this is measured.
- PBA-s total score change from baseline to each visit that this is measured.
- Q-motor assessments (digitomotography, dysdiadochomotography, manumotography and choreomotography, and pedomotography) change from baseline to each visit that this is measured.

All efficacy endpoints will be summarized for actual values and changes from baseline to each visit using descriptive statistics.

PBA-s domain scores will also be summarized for actual values and changes from baseline of this study to each visit using descriptive statistics.

No formal inferential statistics will be applied to the efficacy endpoints. Efficacy analyses will be considered exploratory.

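### SAP 4.4 fills a missing UHDRS-TFC item with the raw mean of the other four although the items have maxima of 2 or 3, so impossible item values and totals can arise (minor correction)

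*SAP*

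**What the plan says.** SAP 4.3 describes the scale. On the items it says "Scores on each item range from 0 to either 2 or 3", and on the total, "The 5 items are summed to yield a TFC total score, which ranges from 0 to 13, with greater scores indicating higher functioning". Occupation is the only item whose categories are written out, as 0 to 3 in whole points.

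SAP 4.4 sets the item-level rule. Its condition is "For the TFC scale of the UHDRS, if responses to 1 item up to 25% of items are missing", and in that case "the missing responses will be replaced by the average of the remaining responses within the TFC scale". Above 25% the total is set to missing. The rule has no cap at the item or scale maximum, no rounding and no weighting by item maximum.

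SAP 6.2 lists the endpoint as "UHDRS-TFC change from baseline to each visit that this is measured", summarised descriptively as actual values and changes. SAP 4.1 includes the minimum and maximum among the descriptive statistics. The protocol names the five TFC domains (Section 6.1.3) but gives no TFC scoring or item-level missing-data rule.

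**The concern.** Filling a missing item with the mean of the others treats all items as sharing one range. That is true of two other scales given the same rule: every UHDRS-TMS assessment is rated 0 to 4 (Protocol 6.1.1), and every mPPT item has a maximum of 4 (SAP Appendix A). It is not true of TFC, on the SAP's own description.

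The replacement can therefore be a value the item cannot take, and the total can fall outside the range that SAP 4.3 gives. If an item is missing at only one of baseline and follow-up, part of the reported change comes from the scoring rule and not from the patient. TFC addresses overall patient function, which is a secondary objective, and a total above 13 would be visible as the maximum in a summary table.

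**Working it through.** **Inputs.** Five items, maxima of 2 or 3, total 0 to 13 (SAP 4.3). Up to 25% of items may be missing, and the replacement is the unweighted mean of the observed items (SAP 4.4).

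**Reproducing the stated range.** Let a items have maximum 3 and b have maximum 2. Then a + b = 5 and 3a + 2b = 13, so a = 3 and b = 2. The maximum is 3×3 + 2×2 = 13, as stated. The SAP does not say which domains have maximum 2, but nothing below depends on that.

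**How many items may be missing.** 1/5 = 20% is within 25%; 2/5 = 40% is not. The rule therefore acts on exactly one missing item.

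**The rule as a formula.** With observed sum R, total = R + R/4 = 1.25R. With true total S and true value x of the missing item, R = S − x, so

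error = 1.25(S − x) − S = 0.25S − 1.25x.

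**Patient at ceiling (S = 13).**

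| Missing item | R | Value filled in | Total | Error |
|---|---|---|---|---|
| maximum 2 | 11 | 11/4 = 2.75 | 13.75 | +0.75 |
| maximum 3 | 10 | 10/4 = 2.50 | 12.50 | −0.50 |

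If the item is missing at follow-up only, an unchanged patient shows a change of +0.75 or −0.50. If it is missing at baseline only, the signs reverse.

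**Uniform fraction f of every maximum (S = 13f).** A missing 2-point item (x = 2f) gives 3.25f − 2.5f = +0.75f. A missing 3-point item (x = 3f) gives 3.25f − 3.75f = −0.50f. At f = 0.5 these are +0.375 and −0.25. Because items are scored in whole points, intermediate f is best read as a group average.

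**When values become impossible.**
- A 2-point item is given more than 2 when R/4 > 2, that is, when R is 9, 10 or 11.
- The total exceeds 13 only when R = 11, since R = 10 gives 12.5. R = 11 requires a 2-point item to be missing and the other four to be at maximum. The total is then always 13.75.
- A 3-point item is given at most 10/4 = 2.5, so never its maximum.

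**Full enumeration.** There are 4³ × 3² = 576 item patterns and 5 choices of missing item, so 2,880 combinations. The total exceeds 13 in 6 of them. The filled value exceeds the item's maximum in 90 of the 1,152 combinations with a 2-point item missing. With all patterns weighted equally (an assumption, not patient data), the mean error is +0.375 for a missing 2-point item and −0.25 for a missing 3-point item.

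**Average over which item is missing.** If each item is equally likely to be missing, the mean of x is S/5 and the mean error is 0.25S − 1.25 × S/5 = 0 for every profile. At ceiling: (2 × 0.75 − 3 × 0.50)/5 = 0.

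**Prorating by item maxima.** Total = R × 13 / (sum of maxima of the observed items). At ceiling this gives 11 × 13/11 = 13 and 10 × 13/10 = 13. It cannot exceed 13, and its error is zero for uniform profiles. Over the 2,880 equally weighted combinations, however, the root mean square error falls only from 1.17 to 1.13 and the mean absolute error from 0.97 to 0.95. The largest error is 3.0 under both rules.

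**The case against.** The strongest case against acting is that the consequence is small. Efficacy is exploratory and descriptive, in a single-arm study whose primary objective is safety and tolerability, and no decision rule uses TFC. Out-of-range totals are a corner case. For scale only: if 2% of records lacked one item (assumed) and every one carried the +0.75 error, a visit mean would move by 0.02 × 0.75 = 0.015 points. All of this stands, and it limits the point to a minor correction. It does not make the rule coherent with SAP 4.3.

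Three stronger readings are tempting, and the documents do not support them.

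- **That mean TFC change is biased.** The errors cancel when items are equally likely to be missing. A net shift needs missingness that is uneven across items and related to their range or score, or that differs between baseline and the visit. Neither document says anything on this.
- **That the large errors for uneven profiles come from the unequal maxima.** Take a 3-point item that is truly 0 but missing, with the rest at maximum. The SAP rule gives 12.5 against a true 10, but prorating by maxima gives 13. The error there is that of filling in from other items at all.
- **That the rule is refuted by the opening of SAP 4.4, "there is no plan to estimate missing data".** That sentence can be read as covering missing visits, with the item-level scoring rules following it explicitly. If it were a contradiction, it would apply equally to UHDRS-TMS, mPPT, SF-12 and PBA-s, so it gives no reason to change TFC alone.

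**Conclusion.** The point holds as a minor correction. On the SAP's own figures, the TFC replacement rule can assign an item a value above its maximum and can produce a total of 13.75 on a scale that ends at 13. It cannot restore a missing 3-point item to its maximum. For an unchanged patient at ceiling with one item missing at follow-up only, the artefact is +0.75 or −0.50 points; at a uniform fraction f of maximum it is +0.75f or −0.50f.

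These individual-level figures follow from the stated item maxima and from the absence of any cap, rounding or weighting. The effect on group means cannot be sized, because the rate and pattern of missing items are not given. It is zero on average under equal item missingness and is probably small otherwise.

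**What to change.** In SAP 4.4, replace the TFC rule with one sentence: the UHDRS-TFC total is set to missing if any of its five items is missing. The cost is that records with one missing item drop out of the TFC summary at that visit, and TFC would no longer share the 25% tolerance given to the other rating scales in the section.

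If the sponsor prefers to keep those records, prorate by item maxima: observed sum × 13 / (sum of maxima of the observed items). This loses no records with a single missing item, keeps totals within 0 to 13 and removes the error for uniform profiles. It does not remove the general error of mean substitution for uneven profiles. The SAP would also need to list the maximum of each item.

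Either change is about one sentence and one line of code, and SAP 2.5.2 provides for amendments approved before database lock.
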